2 SYNOPSIS

Name of Sponsor: Cumberland Pharmaceuticals	Name of Finished Product: Ifetroban Capsules	Name of Active Ingredient: ifetroban
Title of Study: A Randomized, Double-Blind, Placebo-Controlled, Multiple Dose Study with an Open-Label Extension to Determine the Safety, Pharmacokinetics and Efficacy of Oral Ifetroban in Subjects with Duchenne Muscular Dystrophy		
Study Centers (Planned): Ten Phase of Development: II		
Expected Study Duration (per subject): Screening period (12 weeks) + Treatment period (12 months) + Open-label Extension (repeatable periods of 12 months)		
Objectives: Primary Study Objective 
Assess the safety of oral ifetroban in male subjects with Duchenne Muscular Dystrophy (DMD) Secondary Study Objectives 
Evaluate the pharmacokinetics and efficacy of oral ifetroban. Exploratory Study Objectives 
Evaluate novel biomarkers for diagnosis and monitoring of cardiomyopathy in DMDEvaluate changes in daily life activity and quality of life		
Methodology: This is a randomized, double-blind, placebo-controlled, multiple dose study with an open-label extension to determine the safety, pharmacokinetics and efficacy of low or high doses of oral ifetroban compared to placebo in subjects with DMD.		
Number of subjects (planned): A total of 48 DMD subjects will be enrolled: 24 subjects with early stage DMD (LVEF > 45%) and 24 with advance stage DMD (LVEF 35% - 45% or historically documented LVEF 35%-45% and baseline LVEF less than 50%)		
Study Population – Main Selection Criteria Inclusion criteria: 
Males 7 years of age and older with the diagnosis of DMD, defined as phenotype consistent with DMD and either positive genotype, first degree relative with positive genotype, or confirmatory muscle biopsy.Stable dose of oral corticosteroids for at least 8 weeks or has not received corticosteroids for at least 30 days.Stable cardiac function defined as change in left ventricular ejection fraction (LVEF) of < 15% and no heart failure admission over the last 12 months; LVEF 35% or greater by cine cardiac magnetic resonance imaging (MRI) or echocardiography; myocardial damage in one or more left ventricular segments evident by late gadolinium enhancement allowed; concurrent angiotensin-converting enzyme inhibitors (ACEI), beta-blocker (BB) or angiotensin receptor blocker (ARB) therapy allowed (selection of which dictated by clinical care) if started three months or greater from first dose of IMP without change in dose. Aldosterone receptor antagonists (eg. Spironolactone or eplerenone) allowed if started 12 months or greater from first dose of Investigational Medicinal Product (IMP). No changes throughout the study allowed, except in the event of a decline in left ventricular ejection fraction (LVEF) >5% following the baseline CMR as measured by a subsequent CMR		

Name of Sponsor:	Name of Finished Product:	Name of Active Ingredient:
Cumberland Pharmaceuticals	Ifetroban Capsules	ifetroban

at the same center. Should this occur, changes in cardiac medications are allowed on the study.
 
a. Late-stage cohort: Subjects are eligible for the late-stage cohort if the subject has:
 
i. LVEF 35%-45% by cine cardiac magnetic resonance imaging (MRI) or echocardiography orii. historically documented LVEF 35%-45% by cine cardiac magnetic resonance imaging (MRI) or echocardiography and if their baseline MRI is less than 50%. 
4. Subjects aged 18 years and older, informed consent obtained directly. For subjects ages 7-17 years old (yo), both assent from the subject and permission from a parent or guardian.
 
5. AAV-based gene therapy permitted if \geq 2 years from AAV administration and subject has documented cardiac decline defined as >5% decline in LVEF over a 2-year period following AAV administration using consecutive CMRs or echocardiography performed at the same center (must still meet inclusion criterion #3).
		

Exclusion criteria:
 
1. Clinically significant illness other than DMD2. Clinically significant laboratory abnormality not associated with DMD3. Major surgery within six weeks prior to the first dose of study drug, or planned surgery during this study which would interfere with the ability to perform study procedures4. Require antiarrhythmic therapy and/or initiation of diuretic therapy for management of acute heart failure in the last 6 months5. A LVEF of < 35% by CMR and/or fractional shortening of < 15% based on ECHO during screening6. A known bleeding disorder or has received anticoagulant treatment within 2 weeks of study entry7. Allergy to gadolinium contrast or known renal insufficiency defined as abnormal cystatin C or creatinine above the upper limit of normal for age. The male serum reference ranges as follows:8. Age 7-9 years - 0.2-0.6 mg/dL9. Age 10-11 years - 0.3-0.7 mg/dL10. Age 12-13 years - 0.4-0.8 mg/dL11. Age 14-15 years - 0.5-0.9 mg/dL12. Age 16 years or older - 0.8-1.3 mg/dL13. Non-MR compatible implants (e.g. neurostimulator, automatic implantable cardioverter-defibrillator [AICD])14. Subjects who participated in a therapeutic clinical trial within 30 days or five half-lives (whichever is longer) of study entry15. Any other condition that could interfere with the subject's participation		

Investigational Medicinal Product (IMP), dose and mode of administration:
 
Oral ifetroban capsules, Doses:
 
Low Dose: < 35 kg: 50 mg, \geq 35 kg: 100 mg/day
 
High Dose: < 35 kg: 150 mg, \geq 35 kg: 300 mg/day
 
Matching oral placebo capsules
		

Duration of treatment: Twelve months
		

Name of Sponsor:	Name of Finished Product:	Name of Active Ingredient:
Cumberland Pharmaceuticals	Ifetroban Capsules	ifetroban
Endpoints:		
Primary Endpoint: Safety and tolerability (baseline to 12 months): percentage of subjects with one or more treatment emergent adverse event (TEAE)		
Secondary Endpoints:		

• Pharmacokinetics – Peak plasma concentration of ifetroban after administration and its acyl glucuronide metabolite. Time of C_{max} (T_{max}), AUC, Clearance and Elimination half-life ($t_{1/2}$). Dot blots of blood will be collected pre-dose and post-dose at 30, 60 (± 5) minutes; 4, 8 and 24 hours (all ± 30 minutes) on Day 0 (first dose) and pre-dose and at 30 minutes (± 5) post dose on Day 7 (steady-state).• Efficacy of ifetroban over 12 months of dosing
◦ Change from baseline in LVEF using cardiac MRI (CMR);◦ Change from baseline in myocardial strain using CMR;◦ Change from baseline in Pulmonary function test results including peak expiratory flow (PEF), forced vital capacity (FVC), forced expiratory volume in 1 second (FEV1), maximum inspiratory pressure (MIP), and maximum expiratory pressure (MEP);◦ Change from baseline in Pediatric Quality of Life Inventory (PedsQL) results, including the gastrointestinal (GI) module and neuromuscular module (NMM)		
Exploratory Endpoints:		

• Novel biomarkers for diagnosis and monitoring of cardiomyopathy in DMD including but not limited to change from baseline in miRNAs, eicosanoids, claudin-5, CD49d, CPK, hs-Trop, NT-proBNP and structural cardiac magnetic resonance (CMR) results• Change from baseline in daily life activity to evaluate motor function and estimate muscle strength measured by an actigraphy sensor worn for 1 week at baseline, Month 6 and Month 12.• Change from baseline in Quantitative Muscle Testing (QMT) to assess muscle strength		
Sample Size: The sample size is based on the comparison of each dose level of ifetroban (Low Dose or High Dose) to placebo with respect to change from baseline in LVEF using CMR for each disease stage, early (LVEF > 45%) or advanced (current/historical LVEF 35% - 45%). Assuming observations from each treatment group have normal distributions with an effect size of 1.6 for the comparison of a dose of ifetroban to placebo, 8 subjects for each treatment group within disease stage will provide power exceeding 85% for a t-test at two-sided level 0.05. Under these assumptions, 8 subjects for each treatment group within disease stage will provide power exceeding 80% for the Wilcoxon rank sum test at two-sided level 0.05. A total of 48 DMD subjects will be enrolled: 24 subjects with early stage DMD (LVEF > 45%) and 24 with advance stage DMD (current/historical LVEF 35%-45%). Assuming a dropout rate of 25%, 60 subjects will be recruited to meet the target sample size of 48 subjects.		

Name of Sponsor:	Name of Finished Product:	Name of Active Ingredient:
Cumberland Pharmaceuticals	Ifetroban Capsules	ifetroban
Enrollment:		
Subjects will be randomly assigned to one of three oral treatment groups: low-dose ifetroban, high-dose ifetroban or placebo for 12 months based on weight within each disease stage, early (LVEF > 45%) or advance (current/historical LVEF 35%-45%).		
Low Dose: < 35 kg: 50 mg, ≥ 35 kg: 100 mg/day		
High Dose: < 35 kg: 150 mg, ≥ 35 kg: 300 mg/day		
Analysis Population:		
All subjects who receive at least one dose of study medication will be included in the Safety Population. All safety data will be summarized for subjects in the Safety Population.		
The Intent-To-Treat (ITT) Population will consist of all treated subjects with at least one post-baseline assessment. The Per Protocol (PP) Population will consist of all subjects in the ITT population with no major protocol violations, including violation of inclusion or exclusion criteria or insufficient dosing where the latter includes missing more than 2 consecutive weeks of dosing for any reason or missing >20% of prescribed doses between visits. Summary statistics will be presented for both the ITT and PP Populations.		
Interim Analysis:		
An early analysis will be performed when half the target enrollment has completed the six month visit and assessments. Key findings for the interim analysis will be summarized.		
Historical Comparator Analyses:		
Endpoints collected during both the double-blind and open label portions of the study will be compared with a U.S. Food and Drug Administration (FDA)-funded DMD natural history study (NHS) with similar endpoint design and yearly study visits. NHS data from patients matched by age, baseline LVEF, and background DMD therapy to CPI-IFE-007 study subjects will be used to supplement the placebo arm of the double-blind portion of the study and will be used as the primary comparator for data collected during the open-label extension.		

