11.1 Sample Size Determination

The sample size is based on the comparison of each dose level of ifetroban (Low Dose or High Dose) to placebo with respect to change from baseline in LVEF using CMR for each disease stage, early (LVEF > 45%) or advanced (current/historical LVEF 35-45%). Assuming observations from each treatment group have normal distributions with an effect size of 1.6 for the comparison of a dose of ifetroban to placebo, 8 subjects for each treatment group within disease stage will provide

power exceeding 85% for a t-test at two-sided level 0.05. Under these assumptions, 8 subjects for each treatment group within disease stage will provide power exceeding 80% for the Wilcoxon rank sum test at two-sided level 0.05. A total of 48 DMD subjects will be enrolled: 24 subjects with early stage DMD (LVEF > 45%) and 24 with advance stage DMD (current/historical LVEF 35-45%). Assuming a dropout rate of 25%, 60 subjects will be recruited to meet the target sample size of 48 subjects.

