11.6 Randomization

Subjects will be randomly assigned to one of three treatment groups: low-dose ifetroban, high-dose ifetroban, placebo, using a 1:1:1 randomization ratio. All subjects will be treated with IMP daily for at a minimum of six months and a maximum of 12 months.

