### 3.3.1 Primary Endpoints

Safety Endpoints:

Safety assessment will be based on treatment emergent adverse events (TEAEs), laboratory abnormalities, ECG, vital signs, and physical examination.

- Percentage of subjects with one or more TEAE
- Change from baseline in laboratory variables and incidence of markedly abnormal laboratory values and shifts from baseline of laboratory values.
- Change from baseline in ECG parameters and incidence of abnormal ECG findings.
- Change from baseline in vital signs.

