### **3.5 Randomization**

Subjects will be randomly assigned to one of three treatment groups: low-dose ifetroban 100 mg/day, high-dose ifetroban 300 mg/day or matching placebo, using a 1:1:1 randomization ratio. All subjects will be treated with IMP daily for a minimum of six months and a maximum of 12 months. Approximately 48 subjects shall be randomized to ensure at least 16 subjects per group will be analyzed for efficacy.

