#### **4.4.2 Treatments**

The following treatments will be given in the DB period:

- High Dose Ifetroban
- Low Dose Ifetroban
- Placebo

- Placebo group created from the Natural History dataset (see [Section 4.5](#))
- Overall

The following treatments will be given in the OL period:

- High Dose Ifetroban

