## 7 SAFETY ANALYSIS

Evaluations of safety will be performed on the Safety Analysis Set. The incidence of AEs, laboratory safety test variables, abnormal ECG findings, Vital signs (including weight), Physical examination along with change from baseline will be summarized by visit, treatment group, subgroup and overall.

Study Day 1 for all safety analyses is defined as the date of the first dose of study drug.

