#### **14.3.7 Analysis with Natural History Data**

Multiple analyses will be completed using matched NH subjects as a historical comparator. See [Figure 2](#) below for a detailed analysis diagram.

In the DB study (Baseline to Month 12), the tables will be presented by the following treatment groups:

- ifetroban High
- Placebo with supplemented NH

In the OL study, the tables will be presented by:

[figure not shown]
One year data (Month 12 to Month 24):

- All OL
- High to High ifetroban
- Low to High ifetroban
- Ifetroban (High and Low combined)
- Placebo to High ifetroban
- NH

All study two-year data (Baseline to Month 24):

- High to High ifetroban
- NH

**Figure 2** All Study Analyses Diagram

For both the OL and the DB, demographic and baseline characteristics will be summarized for by treatment group including baseline LVEF, concomitant medication usage and propensity score by treatment group for the DB period and the OL period. Summary tables will be provided for the observed value and the change from baseline for each endpoint. In addition, 95% confidence intervals will be presented for each treatment group for the demographic variables and baseline characteristics. For categorical variables, proportion confidence intervals will be created using the binomial approximation.

A listing of natural history subjects' demographic and baseline characteristics will also be included.

For the DB period, the endpoints CFB in LVEF and myocardial strain at 12 Months. For the OL period, the endpoints to be evaluated at the 24 months after treatment are CFB LVEF, CFB myocardial strain, PET, QMT, and accelerometry. All endpoints will be evaluated using the change from baseline will be compared between the ifetroban vs. Placebo or natural history groups using a Wilcoxon rank sum test

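### Double-blind safety: the only pooled column the SAP names mixes ifetroban with placebo, and no low-plus-high ifetroban estimate is planned for a primary objective about the drug

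*Protocol*

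**What the plan says.** The primary objective in the Protocol synopsis is to "Assess the safety of oral ifetroban in male subjects with Duchenne Muscular Dystrophy (DMD"); Protocol 6.1 and SAP 3.2.1 repeat it. The leading primary endpoint in SAP 3.3.1 is "Percentage of subjects with one or more TEAE".

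SAP 4.4.2 gives the double-blind groups as high dose, low dose, placebo, then "Placebo group created from the Natural History dataset", then Overall. SAP section 7 states that adverse events, laboratory values, ECG findings, vital signs and physical examination "will be summarized by visit, treatment group, subgroup and overall". SAP 7.2 again uses treatment group and overall for laboratory values. SAP 4.1 allows a total where applicable. Protocol 11.8.4 tabulates TEAEs by treatment group and dose level and names no pooled column.

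SAP 7.1 specifies counts and percentages for TEAEs, without a confidence interval or a between-group difference. SAP 6.5 mentions treatment-effect estimates within subgroups and includes the primary endpoint among the outcomes, but it gives no effect measure and no low-plus-high grouping.

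The one place where the two doses are pooled is SAP 14.3.7. There "Ifetroban (High and Low combined") is a column in the Month 12 to Month 24 open-label comparison with natural-history subjects.

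**The concern.** An objective about ifetroban calls for an estimate in everyone randomised to ifetroban, set against placebo. The named columns give two single-dose estimates and one pool that includes placebo. A reader who wants one figure for the drug is offered Overall, and that figure describes neither drug nor placebo.

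What is at stake is precision on the primary objective. The arms are small. Protocol 5.4 says the earlier multi-dose safety studies did not include children, and Protocol 5.5 names bleeding as a potential risk from the mechanism. Doubling the exposed group in a single column uses data that are already collected.

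**Working it through.** **Inputs.** Protocol 11.1: "A total of 48 DMD subjects will be enrolled: 24 subjects with early stage DMD (LVEF > 45"%), with a further 24 at advanced stage. Protocol 11.6: "using a 1:1:1 randomization ratio". SAP 3.5: "Approximately 48 subjects shall be randomized to ensure at least 16 subjects per group will be analyzed for efficacy". Recruitment is 54 in SAP 3.4 (10% dropout) and 60 in Protocol 11.1 (25% dropout). The documents give no adverse event rates, so every rate below is an assumption.

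**Step 1, arm size.** 48/3 = 16, which reproduces the SAP's figure. That figure is an efficacy target, whereas safety counts every dosed subject. If all recruited subjects are dosed, arms are 54/3 = 18 or 60/3 = 20. Combined ifetroban is then 32, 36 or 40.

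**Step 2, what Overall estimates.** With equal arms, Overall = (2/3) × ifetroban rate + (1/3) × placebo rate.

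| Assumed ifetroban | Assumed placebo | Overall |
|---|---|---|
| 12% | 0% | 8.0% |
| 50% | 25% | 41.7% |
| 90% | 70% | 83.3% |

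**Step 3, precision of a single proportion.** If no case is seen in n subjects, the one-sided 95% upper limit is 1 − 0.05^(1/n). The last two columns are exact two-sided 95% intervals around an observed 50%, which is closer to how the any-TEAE endpoint may behave.

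| Dosed per arm | Zero-event limit, one arm | Zero-event limit, combined | 50% observed, one arm | 50% observed, combined |
|---|---|---|---|---|
| 16 | 17.1% | 8.9% | 24.7–75.3% | 31.9–68.1% |
| 18 | 15.3% | 8.0% | 26.0–74.0% | 32.9–67.1% |
| 20 | 13.9% | 7.2% | 27.2–72.8% | 33.8–66.2% |

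**Step 4, precision of the contrast with placebo.** With similar event rates, the ratio of standard errors (2n v n against n v n) is √[(1/n + 1/(2n)) / (2/n)] = √0.75 = 0.866, or 13% lower at any n. If rates differ, the gain depends on which group has the larger variance p(1 − p):
- 50% v 25%: √[(0.1875 + 0.25/2) / (0.1875 + 0.25)] = √0.714 = 0.845, about 15% lower.
- 90% v 70%: √[(0.21 + 0.09/2) / (0.21 + 0.09)] = √0.85 = 0.922, about 8% lower.

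**Step 5, who is in the safety Overall.** SAP 3.6.3 limits the Safety Population to subjects who were dosed, and section 7 analyses safety on that set. Natural-history subjects receive no study dose, so they fall outside it. Their double-blind role in Protocol 11.5 and 11.8.3 and SAP 14.3.7 is in efficacy comparisons. The placebo share of Overall is therefore one third under equal arms.

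**The case against.** The strongest reply is that reporting by dose is a legitimate choice in a dose-ranging study, and that nothing is lost by it. Low, High and Placebo each have a column, all adverse events are listed by subject, and no text says the primary endpoint is judged on Overall. Combined counts can be had by adding two adjacent cells, and pooling can blur a dose trend. The open-label precedent is weak, because by then every subject takes the high dose. The shells might also already contain the column.

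Much of this stands, and it rules out three stronger readings that a reader might infer:
- *Natural-history subjects dilute the safety Overall.* The Safety Population definition excludes them. The list in SAP 4.4.2 is loosely worded, since it presents them as a treatment given in the double-blind period with Overall directly beneath.
- *A signal is hidden or halved.* An event with a 12% rate at both doses has an expected rate of 12% in each dose column; only the count is split.
- *The chance of seeing an event is lower.* For an assumed 5% event, the chance of at least one case is 1 − 0.95^16 = 56% in one arm and 1 − 0.95^32 = 81% in both. Both arms are on the page, so 81% already applies under the current plan.

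What the reply does not answer is narrower. Adding cells gives counts, but not the combined medians of laboratory, ECG and vital-sign changes. It also supplies no prespecified interval or contrast with placebo. Keeping the separate dose columns beside the combined one meets the worry about a dose trend.

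**Conclusion.** The point holds as one of precision and presentation. The only pooled double-blind safety column named in the SAP is one-third placebo, and no combined ifetroban estimate, interval or contrast is named for the primary objective. A combined column roughly halves the zero-event upper limit (17.1% to 8.9% at 16 per arm; 13.9% to 7.2% at 20). It also cuts the standard error against placebo by about 13% at similar event rates.

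These sizes assume equal arms and, for 18 or 20 per arm, that every recruited subject is dosed. The combined figure describes the average over the two doses, and represents each dose only if their rates are alike. The 13% is a large-sample ratio and will not carry over exactly to exact intervals. The table shells were not available, so the conclusion is confined to what the Protocol and SAP name.

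**What to change.** In SAP 4.4.2 and section 7:
- Add an 'All ifetroban (Low + High)' column to every double-blind safety table, beside Low, High and Placebo. Overall may stay for disposition and demographics.
- Report the percentage with one or more TEAEs with an exact 95% confidence interval for each dose, combined ifetroban and placebo.
- Report the TEAE risk difference against placebo, combined and by dose, with exact 95% confidence intervals, and name the method.
- Restrict the natural-history entry in 4.4.2 to the efficacy tables.

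The cost is one extra column in the shells and a short programming addition, with no new data. A combined column read alone could obscure a dose trend, so the separate dose columns must remain.

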7.2 Drugs and Dosages

Oral ifetroban is available as the sodium salt of the free acid and is for investigational use only. The drug is supplied as a capsule dosage form (size # 1, white opaque) for oral administration. Ifetroban capsules are formulated as a dry powder blend and filled into hard gelatin capsules. The formulation consists of ifetroban, mannitol, microcrystalline cellulose, crospovidone, magnesium oxide, colloidal silicon dioxide, and magnesium stearate. Capsules are filled into high density polyethylene bottles and sealed with screw-cap closures. Capsules are only available at one strength of the sodium salt, i.e., 52.5 mg corresponding to a free-acid dose of 50 mg.

Matching placebo capsules are formulated as a dry powder blend filled into capsules. The formulation consists of microcrystalline cellulose, crospovidone, colloidal silicon dioxide, and magnesium stearate. Capsules are filled into high density polyethylene bottles and sealed with screw-cap closures.

The bottles of oral ifetroban or placebo will contain the following information on the label:

PLACEBO OR IFETROBAN CAPSULES 50 MG

Quantity: 75 Capsules

Instruction: Take capsules by mouth as directed.

Store at controlled room temperature, 20°C – 25°C (68°F – 77°F)

Caution: New Drug-Limited by Federal law to investigational use

Cumberland Pharmaceuticals Inc.

Additionally, each individual bottle will be labelled with a unique numeric code that identifies the contents to the unblinded sponsor representative. Subjects will be randomized to low-dose ifetroban, high-dose ifetroban or placebo.

Low Dose: < 35 kg: 50 mg, ≥ 35 kg: 100 mg/day

High Dose: < 35 kg: 150 mg, ≥ 35 kg: 300 mg/day

Table 7-1 Ifetroban Dose Levels & Sub-Groups

DMD Sub-Group	Low Dose	High Dose	Placebo
Early Stage (LVEF > 45%)	8 subjects	8 subjects	8 subjects

DMD Sub-Group	Low Dose	High Dose	Placebo
Advance Stage (current/historical LVEF 35-45%)	8 subjects	8 subjects	8 subjects

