Should a subject experience an intolerable toxicity attributed to study drug the dose may be reduced by 50-mg decrements (one capsule) at a time at the investigator's discretion. Any subject receiving 50 mg/day who experiences an intolerable toxicity attributed to study drug will be discontinued from the study. A subject may also have their dose held for up to two weeks to allow a severe adverse event to improve or resolve before considering resuming drug. IMP may resume at the starting dose or a reduced dose at the investigator's discretion, once the toxicity has improved or resolved. Any subject with a serious toxicity that does not improve or resolve after a two week hold of IMP will be discontinued from the study.

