## 5.3 Dosing and Extent of Exposure

Exposure and compliance will be summarized for the Safety Population by treatment group and overall. Comments recorded on the Study Drug Accountability eCRF page will not be applied in the computation of compliance. Exposure is the duration (days) of treatment, computed as:

Exposure = Date of Final Dose - Date of Baseline Visit + 1.

Treatment compliance will be calculated as:

Compliance (%) = 100\*(Total Number of Capsules Dispensed-Total Number of Capsules Returned)/ (Expected Usage),

where Expected Usage= Exposure \* number of capsules to have been taken daily (1 capsule for 50 mg, 2 for 100 mg, 3 for 150 mg, or 6 for 300 mg).

Summary statistics for exposure and compliance will be presented in a table with the corresponding listing for the Safety Population. The number of subjects fasted at time of IMP administration for Month 6, Month 12 and both Month 6 and Month 12 will be summarized as categorical data (yes/no, %).

A subject-data listing of compliance will be provided.

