### 7.1 Adverse Events

The AE verbatim descriptions (investigator terms from the CRF) will be classified into standardized medical terminology using the MedDRA. Adverse events will be coded to the MedDRA (Version 27.0 or higher) LLT closest to the verbatim term. The linked MedDRA PT and primary SOC will also be captured in the database.

A treatment-emergent adverse event (TEAE) will be defined as an AE that starts during or after dosing or starts prior to dosing and increases in severity after dosing.

A treatment related AE will be defined as an AE with a relationship of possible, probable, unlikely, or unrelated to the study treatment, as determined by the investigator.

All AEs will be listed. In addition to the data recorded in the database, the listings will include derived onset time and duration. Onset time will be calculated from the time of dosing for TEAEs only.

The frequency of subjects with TEAEs/serious adverse events (SAEs) and the number of TEAEs/SAEs will be summarized for the following categories:

- TEAEs/SAEs (overall, serious, leading to discontinuation, and leading to death)
- TEAEs by severity
- Treatment-related AEs/SAEs (overall, serious, leading to discontinuation, and leading to death)
- Treatment-related AEs by severity
- TEAEs leading to discontinuation of study drug.
- TEAEs by SOC and PT.
- TEAEs by PT

A subject will be counted only once within a SOC and PT, even if the subject experienced more than one TEAE within a specific SOC and PT. The number (percentage) of subjects with TEAEs will also be summarized by maximum severity (mild, moderate, or severe). The number (percentage) of subjects with TEAEs will also be summarized by relationship to study drug (related and not related).

For the AE data the following rules will apply:

- For the derivation of treatment-emergent status (applicable to all AEs): If the start date/time of an AE is incomplete or missing, an AE will be assumed to be a TEAE, unless the incomplete start date/time or the end date/time indicates an AE started after dosing.
- For the derivation of treatment-related status (applicable to TEAEs only): If the study treatment relationship for a TEAE is missing, a TEAE will be assumed to be a treatment-related TEAE.

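### No planned summary counts dose reductions or holds, and the reduction steps before mandatory discontinuation differ by arm, so the discontinuation table is not a like-for-like comparison of tolerability

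*Protocol*

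**What the plan says.** **Endpoint.** The protocol synopsis defines the primary endpoint as "Safety and tolerability (baseline to 12 months): percentage of subjects with one or more treatment emergent adverse event (TEAE". SAP 3.3.1 lists "Percentage of subjects with one or more TEAE" and adds laboratory, ECG and vital-sign measures. Neither includes a dose-modification measure.

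**Doses (Protocol 7.2).** "Low Dose: < 35 kg: 50 mg, ≥ 35 kg: 100 mg/day"; "High Dose: < 35 kg: 150 mg, ≥ 35 kg: 300 mg/day". SAP 3.5 names only 100 and 300 mg/day. SAP 5.3 nevertheless lists the capsule counts for all four doses, so I use the protocol's weight bands; SAP 3.5 should be reconciled with them.

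**Handling of intolerance (Protocol 7.2).** For intolerable toxicity, "the dose may be reduced by 50-mg decrements (one capsule) at a time", at the investigator's discretion. At the bottom of the range, "Any subject receiving 50 mg/day who experiences an intolerable toxicity attributed to study drug will be discontinued from the study". A dose may also be held for up to two weeks. Serious toxicity that has not improved or resolved after such a hold means discontinuation at any dose.

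**Planned summaries.** SAP 7.1 tabulates TEAEs by severity, relationship, SOC and PT, and "TEAEs leading to discontinuation of study drug". SAP 5.1 covers early termination with its reason. In SAP 5.3, "Exposure is the duration (days) of treatment, computed as" the final dose date minus the baseline visit date plus one. Compliance is capsules dispensed minus returned, divided by Expected Usage. Expected Usage is exposure times 1, 2, 3 or 6 capsules a day.

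**The concern.** The endpoint is labelled tolerability, but the plan does not report the two actions that the protocol takes first when a boy cannot tolerate the drug. Discontinuation is what remains, and it sits behind a different number of reduction steps in each arm. A reader comparing discontinuations between doses would be comparing boys who may have had up to five reductions with boys who had one or none.

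Protocol 5.4 says the earlier multi-dose safety studies did not include children and gives this as the reason for comparing two dose ranges. The open-label extension then uses high dose throughout. How well boys stay on the high dose is therefore something readers will want from this trial, and a discontinuation table alone could mislead them.

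**Working it through.** **1. Steps before the 50 mg/day rule applies.** Capsules = dose/50; steps = (dose − 50)/50. The capsule counts reproduce the 1, 2, 3 and 6 stated in SAP 5.3.

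| Weight | Low dose | Steps | High dose | Steps |
|---|---|---|---|---|
| < 35 kg | 50 mg (1 capsule) | 0 | 150 mg (3) | 2 |
| ≥ 35 kg | 100 mg (2) | 1 | 300 mg (6) | 5 |

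The number of placebo capsules is not stated, so the placebo arm's steps cannot be derived.

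**2. What this does to discontinuation.** Let t(d) be the chance of intolerable toxicity at dose d, and r the share of such episodes handled by reduction rather than stopping. Then D(50) = t(50) and D(d) = t(d) × [(1 − r) + r × D(d − 50)]. The documents give neither t nor r, so the following are assumptions: t = 5% at 50 mg, 10% at 100, 15% at 150, 20% at 200, 25% at 250 and 30% at 300; half of each arm in each weight band. The hold route and withdrawal of consent are left out.

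Example at r = 0.9: D(100) = 0.10 × (0.1 + 0.9 × 0.05) = 1.45%; D(150) = 0.15 × (0.1 + 0.9 × 0.0145) = 1.70%. Continuing upwards, D(300) = 3.8%.

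| r | < 35 kg: low v high | ≥ 35 kg: low v high | Whole arm: low v high |
|---|---|---|---|
| 1 | 5.0% v 0.08% | 0.5% v 0.001% | 2.8% v 0.04% |
| 0.9 | 5.0% v 1.7% | 1.5% v 3.8% | 3.2% v 2.8% |
| 0.75 | 5.0% v 4.1% | 2.9% v 9.1% | 3.9% v 6.6% |
| 0.5 | 5.0% v 7.9% | 5.3% v 17.1% | 5.1% v 12.5% |
| 0 | 5.0% v 15.0% | 10.0% v 30.0% | 7.5% v 22.5% |

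The whole-arm figure is the mean of the two bands, e.g. at r = 0.9, (1.70 + 3.82)/2 = 2.8%. At r = 1, D(300) = 0.05 × 0.10 × 0.15 × 0.20 × 0.25 × 0.30 = 0.00001.

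The last row is also the share with intolerance at the assigned dose. A composite of reduction or discontinuation would show 7.5% v 22.5% whatever r is. Discontinuation alone ranges from a reversed order to the full difference.

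**3. Two other assumptions.**
- Every episode is handled by reduction and each level carries the same independent 30% risk. Discontinuation is then 0.30^(steps + 1): 30% and 9% at low dose, 2.7% and 0.07% at high dose. With 16 per arm split equally, that is about 3.1 low-dose against 0.2 high-dose boys.
- Each boy has a fixed tolerated dose and reduction is always used. Only boys who cannot take 50 mg discontinue, so both arms have the same expected rate and a dose effect is hidden without favouring either arm.

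**4. What exposure and compliance would show.**
- *Hold.* A 14-day hold in 365 days leaves exposure at 365. Compliance is (365 − 14)/365 = 96.2%. It does not exceed the per-protocol limit of more than two consecutive weeks.
- *Large reduction.* 300 to 100 mg after Month 1 means (1 × 6 + 11 × 2)/(12 × 6) = 28/72 = 38.9% against the assigned dose, and 28/28 = 100% against the dose in force at the time.
- *One step.* 300 to 250 mg at mid-year means (6 × 182 + 5 × 183)/(6 × 365) = 2007/2190 = 91.6%, or 100%. Five capsules a day is not among the listed counts.

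The formula does not say which denominator applies.

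**The case against.** The strongest reply is that the plan already captures more than this suggests. The listed capsule counts match the four starting doses exactly. Read literally, Expected Usage is then the assigned dose, and compliance already shows delivered dose as a percentage of it. Any toxicity that leads to a reduction is a TEAE, so it enters the primary percentage and the severity tables. Protocol section 11 says all recorded data will be listed, SAP 5.1 summarises reasons for per-protocol exclusion, and the table shells are in a separate document that may contain more.

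Most of this stands as a limit on the point, but it does not remove it. The literal reading of Expected Usage is plausible but not stated, and one compliance figure cannot separate a reduction from missed capsules. Severity tables do not show whether the dose was changed. The SAP 7.1 definition of a treatment-related event also takes in unlikely and unrelated events, so as worded those tables do not isolate drug intolerance. Listings are not between-arm summaries. The unseen shells mean that the claim is confined to the protocol and SAP.

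A reader might infer that the discontinuation table will favour the high dose. The documents do not support that. Reduction is discretionary, unresolved serious toxicity after a hold ends treatment at any dose, and subjects may withdraw for other reasons. The illustrations give a lower, equal or higher high-dose rate depending on assumptions. In the ≥ 35 kg band the order is reversed at r = 1 but no longer at r = 0.9.

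The 300-to-100 mg example needs four one-capsule decrements. It illustrates the formula and is not an expected case.

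**Conclusion.** The point holds in a limited form. No summary planned in the protocol or SAP counts subjects with a dose reduction or hold. The step counts (5 and 2 against 1 and 0) follow directly from the documents, so discontinuation alone is not a fair comparison of tolerability between doses and can mask or reverse a difference. The percentages above rest on assumed risks, an assumed use of reduction and an equal weight split; they show what is possible and do not predict the result.

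It would also be wrong to infer that the any-TEAE primary percentage is biased: a TEAE that leads to a reduction still counts. The gap is in what supports the word tolerability, together with an undefined compliance denominator. With 16 per arm the amounts are a few boys: 22.5% is 3.6 and 7.5% is 1.2. This is a cheap improvement to reporting and does not call the design into question.

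**What to change.** **SAP 7.1.** Add the number and percentage of subjects with a TEAE leading to dose reduction, dose hold or discontinuation, as a composite and by component, by arm and weight band. State that discontinuation alone is not comparable across arms because the available reduction steps differ.

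**SAP 5.3.** Report days held. Define Expected Usage on the dose assigned at randomisation, so that compliance shows delivered dose as a percentage of assigned dose. Optionally show it also against the dose in force, which separates reductions from missed capsules.

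**Cost.** SAP wording and two tables. It must be confirmed that the CRF records the action taken with study drug for each adverse event; the documents do not show this. Estimates will be imprecise: 4 of 16 has a 95% half-width of about 1.96 × √(0.25 × 0.75/16) = 21 percentage points, and weight-band figures are wider still, so those are descriptive. The high dose may look less favourable than under discontinuation alone. The dose-modification rules stay as they are.
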